3.1.1.2 Non-target lesions and new lesions

At each visit, an overall assessment of the NTL response should be recorded by the Investigator. [Table 5](#) provides the definitions of the criteria used to determine and record overall response for NTLs at the investigational site at each visit. Non-target lesion response will be derived based on the investigator's overall assessment of NTLs.

Table 5 NTL visit responses

Visit Responses	Description
CR	Disappearance of all NTLs since baseline. All lymph nodes must be non-pathological in size (<10 mm short axis).
Non CR/Non PD	Persistence of one or more NTLs (with no evidence of progression).
PD	Unequivocal progression of existing NTLs. Unequivocal progression may be due to an important progression in one lesion only or in several lesions. In all cases, the progression MUST be clinically significant for the physician to consider changing (or stopping) therapy.
NE	Only relevant when one or some of the NTLs were not assessed and, in the Investigator's opinion, they are not able to provide an evaluable overall NTL assessment at this visit. Note: For patients without TLs at baseline, this is relevant if any of the NTLs were not assessed at this visit and the progression criteria have not been met.
NA	Only relevant if there are no NTLs at baseline.

Abbreviations: CR = Complete response; NA = Not applicable; NE = Not evaluable; PD = Progressive disease; NTL = Non-target lesion.

To achieve 'unequivocal progression' on the basis of NTLs, there must be an overall level of substantial worsening in non-target disease such that, even in presence of SD or PR in TLs, the overall tumour burden has increased sufficiently to merit a determination of progression. A modest 'increase' in the size of one or more NTLs is usually not sufficient to qualify for unequivocal progression status.

Details of any new lesions will also be recorded with the date of assessment. The presence of one or more new lesions is assessed as progression.

A lesion identified at a follow-up assessment in an anatomical location that was not scanned at baseline is considered as a new lesion and will indicate disease progression.

The finding of a new lesion should be unequivocal: ie, not attributable to differences in scanning technique, change in imaging modality, or findings thought to represent something other than tumour.

If a new lesion is equivocal, for example because of its small size, the treatment and tumour assessments should be continued until the new lesion has been confirmed. If repeat scans confirm there is a new lesion, then the progression date should be declared using the date of the initial scan.

New lesions will be identified via a Yes/No tick box. The absence and presence of new lesions at each visit should be listed alongside the TL and NTL visit responses.

A new lesion indicates progression, so the overall visit response will be PD irrespective of the TL and NTL response.

If the question ‘Any new lesions since baseline’ has not been answered with Yes or No and the new lesion details are blank, this is not evidence that no new lesions are present and should be treated as NE in the derivation of overall visit response.

Symptomatic progression is not a descriptor for progression of NTLs or TLs: it is a reason for stopping study therapy and will not be included in any assessment of NTLs or TLs.

Patients with ‘symptomatic progression’ requiring discontinuation of treatment without objective evidence of disease progression at that time should continue to undergo tumour assessments, where possible, until objective disease progression is observed.

3.1.1.3 Overall visit response

[Table 6](#) defines how the previously defined TL and NTL visit responses will be combined with new lesion information to give an overall visit response.

Table 6 Overall visit response

Target lesions	Non-target lesions	New lesions	Overall visit response
CR	CR (or NA)	No (or NE)	CR
CR	Non CR/Non PD or NE	No (or NE)	PR

PR	Non PD or NE or NA	No (or NE)	PR
SD	Non PD or NE or NA	No (or NE)	SD
PD	Any	Any	PD
Any	PD	Any	PD
Any	Any	Yes	PD
NE	Non PD or NE or NA	No (or NE)	NE
NA	CR	No (or NE)	CR
NA	Non CR/Non PD	No (or NE)	SD
NA	NE	No (or NE)	NE
NA	NA	No (or NE)	NED

Abbreviations: CR = Complete response; NA = Not applicable (only relevant if there were no NTLs at baseline); NE = Not evaluable; NED = No evidence of disease; NTL = Non-target lesion; PD = Progressive disease; PR = Partial response; SD = Stable disease.

3.2 Efficacy variables

3.2.1 Primary endpoint

The primary endpoint is the proportion of patients with a given genetic and proteomic marker (including, but not limited to, EGFR mutations, HER2, and cMET expression and/or amplification) at the point of RECIST disease progression as defined by the Investigator; the choice of markers is dependent on the profile comparison at the point of disease progression and prior to treatment initiation. The number of patients with a given genetic and proteomic marker will be divided by the number of patients who have evaluable paired biopsies and have progressed according to the Investigator to calculate the proportion with a given marker at progression. New markers will be defined (for an individual patient) to be those present at progression that were not present at baseline. Only markers defined as 'Pathogenic', 'Likely pathogenic' or 'Ambiguous' by the analysing lab will be tabulated.

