Marker Frequency	95% confidence interval ^a
10%	(3%, 22%)
30%	(18%, 45%)
50%	(36%, 64%)

^a Exact binomial confidence intervals.

If a patient progresses in the ELIOS study and then enrols in a subsequent AZ study, and if appropriate consent is provided, the biomarker results from a progression biopsy (generated in either the other study or ELIOS), may be shared between both studies and the data may be analysed as part of the ELIOS study.

The primary data analysis set will include all patients with evaluable paired biopsies. This analysis set will be used for the analysis of the primary endpoint. The full analysis set will include all patients who receive at least one dose of osimertinib and will be used for all other efficacy and safety analyses.

The number of patients with a given tumour genetic and proteomic marker will be divided by the number of patients who have evaluable biopsies and have progressed according to the Investigator to calculate the proportion with a given marker at progression. Exact binomial 95% confidence intervals will be calculated.

TABLE OF CONTENTS

TITLE PAGE.....	1
VERSION HISTORY	2
CLINICAL STUDY PROTOCOL SYNOPSIS	26
TABLE OF CONTENTS	31
1. INTRODUCTION	40
1.1 Background and Rationale for Conducting This Study	40
1.2 Rationale for Study Design, Doses and Control Groups.....	44
1.3 Benefit/Risk and Ethical Assessment	45
1.4 Study Design.....	45
1.4.1 Study conduct mitigation during study disruptions due to cases of civil crisis, natural disaster, or public health crisis.....	47
2 STUDY OBJECTIVES.....	48
2.1 Primary Objective	48
2.2 Secondary Objectives.....	48
2.3 Safety Objective.....	49
2.4 Exploratory Objective	49
3 PATIENT SELECTION, ENROLMENT, RESTRICTIONS, DISCONTINUATION AND WITHDRAWAL.....	49
3.1 Inclusion Criteria	49
3.2 Exclusion Criteria	51
3.3 Patient Screening and Enrolment.....	55
3.4 Procedures for Handling Incorrectly Enrolled Patients	55
3.5 Restrictions	55
3.6 Discontinuation of Investigational Product.....	57
3.6.1 Procedures for discontinuation of a patient from investigational product	58
3.7 Criteria for Withdrawal	58
3.7.1 Screen failures	58
3.7.2 Withdrawal of informed consent	59
3.8 Discontinuation of the Study	59
4 STUDY PLAN AND TIMING OF PROCEDURES.....	59
4.1 Screening/Enrolment Period.....	59

4.2	Treatment Period.....	65
4.2.1	Cycle 1 to 6 inclusive.....	65
4.2.2	Cycle 7 and subsequent cycles	65
4.2.3	Treatment discontinued.....	65
4.3	Follow-up Period	65

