8.3 Definitions of Analysis Sets

The primary analysis set (PAS) will include all patients with evaluable paired biopsies. This analysis set will be used for the analysis of the primary endpoint. The full analysis set will include all patients who receive at least one dose of osimertinib and will be used for all other efficacy and safety analyses.

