8.3.1 Primary analysis set

The PAS will include all patients with evaluable paired biopsies, which are defined as follows: the first biopsy taken prior to osimertinib treatment and the second biopsy taken at any time between Investigator-assessed, RECIST 1.1-defined progression and before the start of any new anticancer treatment. If the Investigator judges the patient to have progressed but the programmatically defined RECIST progression does not occur, the patient will still be considered evaluable. This analysis set will be used for the analysis of the primary endpoint.

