8.4 Outcome Measures for Analyses

8.4.1 Calculation or derivation of primary endpoint variables

The primary endpoint is the proportion of patients with a given genetic and proteomic marker (including, but not limited to, EGFR mutations, HER2, and cMET expression and/or amplification) at the point of disease progression as defined by the Investigator; the choice of markers is dependent on the profile comparison at the point of disease progression and prior to treatment initiation. The number of patients with a given genetic and proteomic marker will be divided by the number of patients who have evaluable biopsies and have progressed according to the Investigator to calculate the proportion with a given marker at progression.

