4.2.2 Attrition of biopsy samples

To explore why patients who had an evaluable baseline did not have a paired progression sample for the primary analysis, the total number of patients that had a baseline biopsy, the number of patients that had a baseline biopsy that was not evaluable, and the number of patients that had an evaluable baseline biopsy will be summarised. The number of patients that had not progressed at DCO, withdrew from the study prior to progression, died prior to progression, did not have a biopsy after progression, had a progression biopsy that was not evaluable, or had an evaluable progression biopsy will be further summarised for patients that had an evaluable baseline biopsy.

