4.2.9.1 Proportion of patients with a given marker

The proportion of patients with a given genetic and proteomic marker at the point of disease progression (as defined by the investigator) will be calculated and presented alongside the associated exact binomial 95% Clopper-Pearson (exact) confidence intervals (CIs).

If a reasonable proportion (at least 20%) of patients have a given marker at baseline, the difference in the proportion of patients with that marker between progression and baseline, together with its 95% adjusted Wald CI, may also be calculated.

The primary analysis table will include the frequency and proportion of new pathogenic, likely pathogenic or ambiguous mutations and will be split by gene name and variant-type. Other tables will follow the same layout but will look at pathogenic, likely pathogenic or ambiguous mutations at baseline and all pathogenic mutations at disease progression. New markers will be defined (for an individual patient) to be those present at progression that were not present at baseline. Only markers defined as 'Pathogenic', 'Likely pathogenic' or 'Ambiguous' by the analysing lab will be tabulated.

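### The table of all mutations at progression needs no baseline sample but is limited to baseline–progression pairs; a supplementary version in all evaluable progression biopsies should be added

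*SAP*

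**What the plan says.** **Denominator.** SAP 3.2.1 gives the endpoint as the proportion of patients with a marker at progression: the count with the marker "divided by the number of patients who have evaluable paired biopsies and have progressed according to the Investigator". Protocol 8.4.1 has almost the same sentence without the word *paired*: "divided by the number of patients who have evaluable biopsies and have progressed according to the Investigator". The statistical methods part of the protocol synopsis also omits it: "by the number of patients who have evaluable biopsies and have progressed according to the Investigator".

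**Analysis set.** Protocol 8.3 states: "The primary analysis set (PAS) will include all patients with evaluable paired biopsies". Protocol 8.3.1 adds: "This analysis set will be used for the analysis of the primary endpoint". SAP 2.1, Table 3 and 4.1 follow this. The only other set, the full analysis set, is for the remaining efficacy and safety analyses.

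**Tables.** SAP 4.2.9.1 states: "The primary analysis table will include the frequency and proportion of new pathogenic, likely pathogenic or ambiguous mutations". New markers are those "present at progression that were not present at baseline" (SAP 3.2.1). The same section plans further tables in the same layout, one for mutations at baseline and one for all pathogenic mutations at progression. It also allows a progression-minus-baseline difference for markers seen in at least 20% of patients at baseline.

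**Attrition.** SAP 4.2.2 counts baseline biopsies and how many of them were not evaluable. It then follows what happened at progression only in patients with a usable baseline: the number who "had an evaluable progression biopsy will be further summarised for patients that had an evaluable baseline biopsy".

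**The concern.** The planned tables answer two different questions. Whether an alteration is *new* can only be decided with a baseline result. Whether an alteration is *present at progression* needs the progression result alone. The SAP uses the paired denominator for both. A patient with a valid progression result therefore drops out of the second table when the baseline assay fails or the baseline sample is missing.

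Evaluable progression tissue is the scarce resource in this trial, and the final data cut-off waits for about 50 pairs. Sequencing of progression tissue is done in real time (protocol 5.4), while baseline tissue is tested later (protocol Table 1, footnote c). The discarded sequencing result would therefore usually exist already, from a mandatory biopsy. EGFR eligibility rests on a local laboratory test (inclusion criterion 5), so a failed central baseline assay does not put the patient outside the target population.

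At stake are some precision and some transparency. The attrition table as planned will not show how many valid progression results were left out for lack of a baseline.

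**Working it through.** **Inputs** (protocol 8.1 and 8.2, SAP 1.3): 70% of patients biopsied at both time points; 30% technical failure; 51% overall failure; 103 of 150 patients progressed at 38 months; exponential progression times with a 19-month median; 100 patients enrolled in months 0–5 and 50 in months 11–12; exact 95% CIs at 50 pairs.

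**Reproducing the plan's figures**
- Pairs: 103 × 0.70 × 0.70 = 50.5 (plan: about 50). Overall failure: 1 − 0.70 × 0.70 = 51%. The plan's arithmetic thus applies the 30% once per pair.
- Progressions at 38 months, with λ = ln 2 / 19 and uniform entry within each recruitment piece: 100 × (1 − 0.274) + 50 × (1 − 0.380) = 72.6 + 31.0 = 103.6 (plan: about 103).
- Clopper-Pearson at n = 50: 5/50 gives 3.3–21.8%, 15/50 gives 17.9–44.6%, 25/50 gives 35.5–64.5%. These agree with the plan's precision table after rounding.

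**Evaluable progression biopsies if pairing is not required**

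Patients biopsied at both times: 103 × 0.70 = 72.1. The documents do not say how the 30% failure divides between the two samples. This is an assumption, so the range is shown with pair success held at 0.70:

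| Assumed location of the 30% failure | Progression success | Evaluable progression biopsies | Gain over 50 pairs |
|---|---|---|---|
| All at progression | 0.70 | 72.1 × 0.70 = 50.5 | none |
| Equal and independent at both times | √0.70 = 0.837 | 72.1 × 0.837 = 60.3 | about 10 |
| All at baseline | 1.00 | 72.1 | about 22 |

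The counts cover only patients biopsied at both times. A patient with a progression biopsy but no baseline biopsy would add to them; the documents give no figure for this.

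**Precision for a marker near 30% (exact 95% CI)**

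| n | Observed | CI | Width (points) |
|---|---|---|---|
| 50 | 15/50 | 17.9–44.6% | 26.7 |
| 60 | 18/60 | 18.8–43.2% | 24.4 |
| 72 | 22/72 | 20.2–42.5% | 22.3 |

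The width falls by 26.7 − 24.4 = 2.3 points with an equal split, by 26.7 − 22.3 = 4.4 points at the upper end, and not at all at the lower end.

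**The case against.** **A reader might infer that the SAP narrows the protocol by adding *paired*.** The documents do not support this. The protocol defines the PAS as paired and assigns it to the primary endpoint in the synopsis, 8.3 and 8.3.1. Its analysis trigger and precision table also count pairs. The SAP follows that set. What remains is loose wording inside the protocol.

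**A reader might infer that the primary analysis itself should drop the pairing.** It should not. The objective is a comparison with the pre-treatment profile, and the table named as primary counts new alterations. A patient without a baseline cannot be classified there. Pairing also keeps the baseline, progression and new-marker tables on the same patients. The point applies only to the table of all mutations at progression.

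**A reader might take the 30% as the failure rate of each sample.** That would give 103 × 0.70 × 0.70 × 0.70 = 35 pairs against 50 progression biopsies, and a larger gain. It contradicts the plan's stated 51% overall failure and its 50 pairs, so it is not used here.

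**A reader might infer that dropping unpaired patients is harmless, or that it causes bias.** The documents do not say whether baseline failure is related to the profile at progression, so neither can be claimed.

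**The attrition table answers its own stated question**, namely why patients with a usable baseline lack a usable progression sample, and it does show how many baselines failed. That stands. It still does not say how many of those patients had a valid progression result.

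**The gain is modest and may be nil.** That also stands, and it is why an added table is proposed and no change to the primary analysis.

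**Conclusion.** The point holds in a limited form. SAP 3.2.1 and 4.2.9.1, read with 2.1, Table 3 and 4.1, place the marker proportions in the paired PAS. That is correct for new markers and for the difference from baseline, and it agrees with the protocol's PAS. It is unnecessarily restrictive for the proportion with any given marker at progression, where it omits valid results.

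The size is uncertain: from no gain to about 22 more patients, with about 10 under an equal split. The result rests on three assumptions: the plan's 103 progressions and 70% rate of biopsy at both times, the 30% failure applying once per pair, and, for the wider table to estimate the same proportion, baseline failure being unrelated to the progression profile. The primary analysis remains valid. This is an inexpensive improvement in precision and transparency.

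**What to change.** 1. **SAP 3.2.1 and 4.2.9.1:** distinguish *any marker at progression* from *new marker*. Keep the PAS for new or lost markers and for the difference from baseline.
2. **SAP 4.2.9.1:** add one supplementary table giving the proportion with any given marker at progression, with exact 95% CI. Include all patients who progressed per the Investigator and have an evaluable progression biopsy taken before any new anticancer treatment, paired or not. Apply to that biopsy the timing rule the PAS already uses for the second biopsy.
3. **SAP 4.2.2:** add the number of evaluable progression biopsies whose baseline was not evaluable or was missing.
4. **Protocol 8.4.1 and synopsis:** reconcile the denominator wording with the paired PAS in 8.3.1.

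The cost is one extra table, one extra attrition row and a second denominator that must be clearly labelled, so that the supplementary figures are not set against the paired baseline table. The sequencing part needs no new samples. Reporting both denominators lets readers see whether patients without a usable baseline look different at progression.

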3.2.2 Secondary endpoints

From the Investigator's review of the imaging scans, the RECIST tumour response data will be used to determine each patient's visit response according to RECIST 1.1. At each visit, patients will be programmatically assigned a RECIST 1.1 visit response of CR, PR, SD or PD depending on the status of their disease compared with baseline and previous assessments. If a patient has had a tumour assessment, which cannot be evaluated, then the patient will be assigned a visit response of not evaluable (unless there is evidence of progression in which case the response will be assigned as progressive disease).

3.2.2.1 Progression-free survival

PFS is defined as the time from the first dose of osimertinib until the date of RECIST 1.1-defined progression or death (by any cause in the absence of progression) regardless of whether the patient withdraws from therapy or receives another anticancer therapy prior to progression. PFS is calculated in months as follows:

$$PFS = \frac{\text{date of objective disease progression or censoring} - \text{date of first dose of osimertinib} + 1}{30.4375}$$

Patients who have not progressed or died at the date of analysis will be censored at the time of the latest date of assessment from their last evaluable RECIST 1.1 assessment.

However, if the patient progresses or dies after two or more missed visits (126 days), the patient will be censored at the time of the latest evaluable RECIST 1.1 assessment.

Given the scheduled visit assessment scheme (i.e., eight-weekly for the first 3.5 years [D1277] then ten-weekly thereafter) the definition of 2 missed visits will change. Due to a delay in enacting CSP version 5.0 there was some variability in when patients transitioned to 10-weekly visit. However, we will apply the following rules to all patients.

1. If the previous RECIST 1.1 assessment is baseline, then two missing visits will equate to 17 weeks since the previous RECIST 1.1 assessment, allowing for a late visit (i.e., 2×8 weeks + 1 week for a late assessment = 17 weeks [119 days]).
2. If the previous RECIST 1.1 assessment is post baseline and \leq study day 1169, then two missing visits will equate to 18 weeks since the previous RECIST 1.1 assessment, allowing for early and late visits (i.e., 2×8 weeks + 1 week for an early assessment + 1 week for a late assessment = 18 weeks [126 days]).
3. If the previous RECIST 1.1 assessment study day is > 1169 and ≤ 1225 , then the two missed visits occur over the period when the scheduled frequency of RECIST 1.1 assessments changes from eight-weekly to ten-weekly, then this will equate to 21 weeks (i.e., take the average of 8 and 10 weeks which gives 9 weeks and then apply same rationale, hence 2×9 weeks + 1 week for an early assessment + 2 week for a late assessment = 21 weeks [147 days]).
4. If the previous RECIST 1.1 assessment study day is > 1225 (when the scheduling changes to ten-weekly assessments), two missing visits will equate to 24 weeks (i.e., 2×10 weeks + 2 week for an early assessment + 2 week for a late assessment = 24 weeks [168 days]).

If the patient has no evaluable post-baseline visits or does not have baseline data, they will be censored at Day 1 unless they die within two visits of baseline (16 weeks plus 1 week allowing for a late assessment within the visit window).

The PFS time will always be derived based on scan/assessment dates not visit dates.

RECIST 1.1 assessments/scans contributing towards a particular visit may be performed on different dates. The following rules will be applied:

- Date of progression will be determined based on the earliest of the dates of the component that triggered the progression.
- When censoring a patient for PFS, the patient will be censored at the latest of the RECIST assessment/scan dates contributing to a particular overall visit assessment.

Overall visit assessments will be determined for each assessment (scheduled or unscheduled) and will contribute to the derivation of PFS.

Objective progression is defined as at least a 20% increase in the sum of the diameters of the target lesions (compared to previous minimum sum) and an absolute increase of >5 mm, or an overall non-target lesion assessment of progression or a new lesion.

